Submaximal intensity protocol: Resistance will begin with 1 minute of unloaded pedaling followed by a step-increase to 75% of peak workload (or the workload determined at the first visit). Workload will then be held at this intensity until volitional exhaustion or limiting symptoms prevail (e.g. subject cannot continue despite verbal encouragement, or subject is unable to maintain pre-specified pedal cadence despite verbal encouragement). Vital signs will be monitored during the test. We will assess exercise endurance time at 75% peak work rate. We may also assess VO₂ kinetics, including Tau, which is the time needed to reach 63% of the total response amplitude, and describe the rate/slope of VO₂ recovery. We will also assess VO₂ efficiency (total O₂ consumed to total work performed), and the respiratory exchange ratio, amongst other parameters gathered during the exercise tests.

The primary outcome for this submaximal part of the study is the difference in exercise endurance at 75% peak work rate following ketone therapy as compared to placebo.

Electrocardiography

A resting 12-lead ECG and prolonged rhythm strip will be obtained prior to exercise, and will be analyzed for rate, rhythm, intervals, and morphology. Heart rate variability metrics will be computed following KE and following the placebo intervention.

Blood sampling and metabolomic profiling

Standard blood testing is performed at Visit 1 for baseline analysis. This may include a CMP, CBC, NT-proBNP, lipid profile, hemoglobin A1c (approximately 20 mL of blood).

We will draw blood frequently before drug, after drug, and during exercise and recovery for measurements. The lab testing protocols are in **Table 2** with **approximate** times noted for planned lab draws (note: given the multitude of lab draws, missing laboratory draws will not be counted as deviations nor is exact timing required for laboratory draws). At Visit 2 and 3, a tertiary goal of blood sampling is to assess the pharmacokinetic (assess circulating ketone levels resulting from the DeltaG) and pharmacodynamic (assess biologic effects of the DeltaG) impact of DeltaG. BHB will be the primary means of determining therapeutic absorption. We will recreate pharmacokinetic curves including C_{max} (peak serum concentration achieved by drug), T_{max} (time at peak serum concentration), and area under the curve (AUC).

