Blood samples will be stored at -80C for later analysis. We may perform comprehensive metabolomic profiling from this peripheral blood, in addition to other tests.

Table 2. Timing of Laboratory Draws during Study Protocol for Visit 2 and 3 WITHOUT Stable Isotope Infusion

Study Time	Plasma and/or Serum Tube Draw
0-30 minutes (baseline)	Х
60 minutes (intervention given) – blood draw immediately before intervention	X
90 minutes (start of echo)	X

105 minutes (mid-echo)	Х
120 minutes (start of maximal effort exercise)	Х
Every 3 minutes during maximal effort exercise	Х
Standardized draw at 25 Watts (if not already drawn)	Х
Time of exhaustion after maximal effort exercise	Х
Following 15 minutes of rest after completion of peak VO ₂ study recovery and prior to lunch	Х
~160 minutes (1/2 dose of intervention prior to submax CPET – blood draw immediately prior to intervention)	X
~190 minutes (submaximal CPET): At rest, 4 minutes (standardized draw), and time of exhaustion	Х

Total blood drawn at Visit 2 and 3: ~180 mL/visit

Stable Isotope Infusion

A secondary goal of this proposal is to understand the metabolic changes induced by acute ketone administration. As described above, ketones have been shown to reduce glucose utilization in both healthy 10, 24, 44 and disease populations. 45 Systemic substrate utilization can be estimated through indirect calorimetry, using the data from gas exchange (carbon dioxide production rate and oxygen uptake rate) to derive rates of systemic carbohydrate and fatty acid oxidation. 46, 47 Yet systemic measurements do not identify the source of the substrate utilized (i.e. plasma-derived versus intramuscular), which may vary with exercise intensity, gender, and possibly disease state. 48-50 Knowing whether there is a deficit in substrate import, leading to alterations in utilization, could lead to new therapeutic opportunities.

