We estimate that sampling blood for the stable isotope measurements during submaximal exercise will increase the amount of blood drawn by approximately 30 mL/visit (total of 60 mL for Visits 2 and 3).

Table 3. Approximate Timing of Laboratory Draws during Study Protocol for Visit 2 and 3 WITH Stable Isotope Infusion

/II				
Study Time	Plasma and/or Serum Tube Draw			
0-30 minutes (baseline)	X			
60 minutes (intervention given)	X			
90 minutes (start of echo)	X			
105 minutes (mid-echo)	X			
120 minutes (start of maximal effort exercise)	X			
Every 3 minutes during maximal effort exercise	х			
Standardized draw at 25 Watts (if not already drawn)	х			
Time of exhaustion after maximal effort exercise	х			
Following 15 minutes of rest after competion of peak VO ₂ study	х			
Immediately prior to start of stable isotope infusion	X			
10, 20, and 30 min, 40, 50, 55, 60, 65 min after start of the prime/continuous infusion	X			
~200 minutes (1/2 dose of intervention given) *lunch is provided after submaximal CPET	X			
Every 10 min prior to the start of the submaximal CPET (e.g. 10, 20, 30 min after intervention)	X			
~230 minutes (submaximal CPET): At rest, every 2 minutes during exercise, and every 2 min of recovery for 10 minutes	X			
Standardized draw at 4 minutes and at the time of exhaustion (if not already drawn)	x			

Stable Isotope Studies: Total blood drawn at Visit 2 and 3 ~ 210 mL/visit (each visit). Note, if stable isotope infusion being performed, additional blood draws will be performed prior to the start of the infusion and every 10 minutes following infusion. Additionally, after ~1 hour of infusion dense sampling will be done (55 minutes, 60 minutes, and 65 minutes) prior to administration of the intervention. After the intervention, samples will be drawn every 10 minutes until the start of submaximal exercise at which time, blood samples will be drawn approximately every 2 minutes of exercise, at the time of exhaustion, and every 2 min of recovery for 10 minutes. The stable isotope infusion will then be discontinued.

Routine, stress, and strain echocardiography

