- (c) Exercise metabolic data:
 - Ventilatory Threshold (using the average of the V-slope method and the Ventilatory Equivalents method, when available)
 - Respiratory Exchange Ratio assessed at:
 - 25W of exercise during incremental study
 - Peak of the incremental study
 - 4 min during the submaximal study
 - Time of exhaustion during the submaximal study
 - Beta-hydroxybutyrate, glucose, lactate, non-esterified fatty acids, insulin, and glucagon assessed at:
 - 25W of exercise during incremental study
 - Peak of the incremental study
 - 4 min during the submaximal study
 - Time of exhaustion during the submaximal study

- Glucose kinetics during the submaximal study in the subgroup who received stable isotopes during the intervention visits:
 - Glucose rate of appearance
 - Glucose rate of disappearance

Safety Endpoint: Presence of exercise-induced arrhythmias (significant atrial or ventricular arrhythmias)

Physiologic Response to the Intervention: In addition to the primary and secondary outcomes, multiple other physiologic endpoints were collected, with some at multiple timepoints within each visit. For some endpoints, not all measurements occurred at regular intervals, and the number of measurements per subject varied. These analyses will be analyzed similarly to the primary endpoints, but with changes to address the repeated measurements within visits. In some cases, the responses can be summarized using a single summary statistic, e.g. the area under a curve (AUC) or the initial slope, while in other cases the individual measurements are of interest. Mixed effects models may be employed to efficiently answer questions related to outcome variables with repeated measurements.

Subgroup analyses:

- Biological sex
- Baseline peak VO_2 indexed to body weight (above versus below median value)
- Diabetic status (No versus Yes)
- Left ventricular ejection fraction above and below 60%¹

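### The SAP does not say whether the scheduled pre-drink blood samples are used when exploratory exercise metabolites are compared; adjusting for them at the maximal-test time points is a cheap gain in precision of unknown size

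*SAP*

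**What the plan says.** **Sampling.** The Protocol, under Blood sampling and metabolomic profiling, states: "We will draw blood frequently before drug, after drug, and during exercise and recovery for measurements". Table 2 (Visits 2 and 3 without isotope infusion) lists a baseline draw at 0-30 minutes and then "60 minutes (intervention given) – blood draw immediately before intervention". Table 3 (visits with isotope infusion) lists draws at the same two times, but does not repeat that the 60-minute sample precedes the drink. The Protocol also says that "missing laboratory draws will not be counted as deviations nor is exact timing required for laboratory draws".

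**Endpoints.** SAP, Exploratory Endpoints (c), lists "Beta-hydroxybutyrate, glucose, lactate, non-esterified fatty acids, insulin, and glucagon assessed at" four points: 25 W and peak of the incremental test, and 4 minutes and exhaustion of the submaximal test. No pre-drink time point appears.

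**Model.** SAP, Primary Analysis, regresses the ketone-minus-placebo difference on treatment sequence and tests the intercept. SAP, Physiologic Response to the Intervention, carries this over: "These analyses will be analyzed similarly to the primary endpoints, but with changes to address the repeated measurements within visits". It mentions AUC, initial slope and optional mixed models. It does not mention a baseline covariate or change from baseline.

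**The concern.** Pairing removes stable differences between people. It does not remove a participant's starting level on the day, and Visits 2 and 3 are one to four weeks apart. If one day's fasting glucose or NEFA is high and stays high into exercise, the difference goes into the paired contrast as noise. A sample taken before the drink measures that level and cannot have been affected by that visit's treatment.

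The stake is precision on the outcomes meant to explain mechanism, including lactate, which is the hypothesis of Protocol Subaim 1, with about 18 pairs. A second, smaller stake is that the SAP wording leaves raw values, change scores and adjusted values all open. These differ in precision, so the choice is better made before the data are seen.

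**Working it through.** **1. The plan's own figures.** A paired t-test with n = 18 and two-sided 0.05 gives power of 91.5% for a difference of 1 with SD 1.2, and 87.7% for an effect size of 0.78. The SAP states 91% and 88%, so both reproduce. They concern the co-primary endpoints and do not depend on this point. The documents give no power or variance figure for the metabolites.

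**2. Set-up.** For each participant let D be the ketone-minus-placebo difference at an exercise time point, and X the same difference in the pre-drink value. Let r be their correlation, here assumed between 0 and 0.7. Sequence is coded -1/2 and +1/2, with 9 participants per sequence.

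- Plan: D on sequence, 16 df.
- Alternative: D on sequence and X, 15 df.

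**3. Formulas.** The covariate removes a share r² of the variance of D. Estimating its slope costs on average a factor 1 + 1/14 = 15/14.

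- Variance ratio = (1 - r²) × 15/14
- CI-width ratio ≈ √[(1 - r²) × 15/14] × t(15 df)/t(16 df), where t(15)/t(16) = 2.1314/2.1199 = 1.0054

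| r | Variance ratio | CI-width ratio |
|---|---|---|
| 0 | 1.07 | 1.04 |
| 0.3 | 0.98 | 0.99 |
| 0.5 | 0.80 | 0.90 |
| 0.6 | 0.69 | 0.83 |
| 0.7 | 0.55 | 0.74 |

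Simulation with 40,000 runs per value of r agrees to within 0.01. Variance breaks even where 1 - r² = 14/15, so r = √(1/15) = 0.26. Interval width breaks even slightly higher, near 0.28.

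**4. In terms of power.** For an assumed effect of 0.5 SD of the paired difference, the plan's model has 51% power. With the covariate, power is 48%, 52%, 60% and 77% at r = 0, 0.3, 0.5 and 0.7. A simple change from the pre-drink value (variance factor 2 - 2r, assuming equal variance before the drink and at exercise) gives 29%, 39%, 51% and 73%. The change score is therefore worse than the plan's model below r = 0.5, and worse than the covariate throughout this range.

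**5. Validity and centring.** With no treatment effect, the plan's model and the model with X uncentred both reject close to 5% of the time. If X is centred at its sample mean, the intercept goes back to the unadjusted estimate but keeps the smaller residual error. Rejection then rises to about 8% at r = 0.5 and 15% at r = 0.7.

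**6. Missing pre-drink values.** The covariate needs a value at both visits. If missing draws cut 18 pairs to 16 (an assumption), the adjusted interval compared with the unadjusted 18-pair interval is 7% wider at r = 0.3, 3% wider at r = 0.4 and 3% narrower at r = 0.5.

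**The case against.** The case for leaving the SAP alone is substantial.

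- **No bias.** Treatment order is randomized, so the sequence-only contrast is valid, and omitting an optional covariate in a crossover is a legitimate choice. This stands.
- **Exploratory endpoints.** No power is claimed for them, and no co-primary or secondary result rests on them. This stands. Lactate has somewhat more weight through Subaim 1.
- **Unknown r.** Nothing in the documents shows that 0.5 to 0.7 is likely. At 0.3 there is practically no gain, and at 0 there is a small loss. This stands.
- **Submaximal time points.** These samples follow the first dose, a maximal test and a further half-dose. At visits without isotope, lunch also intervenes (Table 2); at isotope visits it comes after the submaximal test (Table 3). Start-of-visit values are probably weaker predictors there. This stands and limits the fix.
- **Using both draws.** The Protocol provides a light breakfast at a time not given in the readable text. If it falls between the draws, averaging mixes fasted and fed values. The tables also name tubes, not assays, so it is an assumption that each analyte was measured before the drink.

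A reader might infer that the SAP rules out the pre-drink values, or that adjusting all four time points is a free gain. Neither is supported. The wording on similar analysis, AUC, slope and mixed models leaves room for a baseline, so the exact statement is that their use is not specified. The gain depends on r and on near-complete samples.

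**Conclusion.** The point holds as a cheap improvement limited to exploratory endpoints; it is not an error in the plan. The samples are scheduled and precede that visit's treatment, and the written model has no term for them. What may be lost is precision: nothing below r of about 0.26 to 0.28, about a tenth of interval width at r = 0.5, and about a quarter at r = 0.7. These figures assume 18 complete pairs, assayed pre-drink values and a linear relation. Co-primary power is unaffected. It would be wrong to read this as biased metabolite comparisons or as a demonstrated large loss of power, since order is randomized and no value of r is given.

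**What to change.** Add to the SAP, for glucose, lactate, NEFA, insulin and glucagon, where the analyte was assayed before the drink:

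1. At 25 W and at peak of the maximal test, include the ketone-minus-placebo difference in the pre-drink value as an additional covariate in the difference model. Enter it uncentred, so that the intercept is the treatment effect at zero pre-drink difference. Do not use a simple change score.
2. Use the 60-minute draw, after confirming that it also precedes the drink at isotope visits. If it is missing, substitute the 0-30 minute draw, preferably at both of that participant's visits so that like is compared with like.
3. Report the unadjusted analysis on all pairs alongside, and state how many pairs lack a pre-drink value.
4. Treat the same adjustment at the two submaximal time points as a sensitivity analysis. The covariate there is still the value before the first drink, because the draw before the half-dose is already post-treatment.
5. Leave beta-hydroxybutyrate unadjusted.

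The cost is a few sentences and one degree of freedom, with no new samples. The downside is intervals about 4% wider if r is near zero, and the loss from the adjusted analysis of any pair without a usable pre-drink value at both visits.

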[figure not shown]

Acute Effects of Exogenous Ketone Ester Administration in Heart Failure

Statistical Analysis Plan

ClinicalTrials.gov Identifier: NCT04633460

Date: February 1st, 2024

[name]

[name], ScD

Study Design: Two-sequence, two-treatment individual-randomized crossover design.

Description of Baseline Characteristics: The demographic and clinical characteristics of the sample will be described overall (intention-to-treat) and by arm using descriptive statistics (means, medians, percentages) with measures of the variation (standard deviation (SD) and interquartile range (IQR)). Graphical procedures will be used to assess distributional assumptions.

Primary Analysis: The primary analysis will regress the difference in outcome for ketone versus placebo on treatment sequence. A Wald test of the intercept will be used for the hypothesis test of a treatment effect. The two co-primary outcomes are:

1. Peak VO_2 during incremental (maximal) exercise testing
2. Time to exhaustion during submaximal exercise testing at 75% peak workload

A type I error rate of 0.05 is pre-specified without correction for multiple comparisons.

Secondary Endpoints: The secondary outcomes will be analyzed using the same model. These are:

1. Percent change in systemic vascular resistance with maximal exercise testing at peak
2. Substrate utilization (reflected by the respiratory exchange ratio) during maximal exercise testing at peak
3. VO_2 efficiency (the ratio of total work performed over oxygen consumed above baseline during exercise, kJ/L of O_2) during submaximal cardiopulmonary exercise testing.

Exploratory Endpoints: Exploratory outcomes will be used to further understand possible mechanisms of action for the change in primary and secondary outcomes, and include several domains:

- (a) Resting echocardiographic data: left ventricular ejection fraction, peak left ventricular global longitudinal strain, e' septal and lateral velocity, E/e' ratio, tricuspid annular planar systolic excursion, and the right ventricular s' velocity.
- (b) Exercise hemodynamic data: Cardiac Output (heart rate x stroke volume), VE/VCO_2 slope, the arteriovenous O_2 content difference (quotient of VO_2 to cardiac output), mean arterial pressure, the vasodilatory reserve, and the mitral E to septal e' ratio assessed at:
 - 25 watts of exercise during incremental study
 - Peak of the incremental study
 - 4 min during the submaximal study
 - Time of exhaustion during the submaximal study

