A term for subgroup will be included in the model described above. A Wald-test of significance will be used to compare to the null value. This analysis is equivalent to the interaction analysis used in the analysis of parallel-group designs. Results will be presented graphically in a forest plot. Subgroup analyses are considered exploratory and thus no formal corrections for multiple comparisons will be used. Rather across the two primary outcomes, and with 4 subgroups, the expected number of tests with a p-value less than 0.05 is 0.4 hypothesis tests. More than one test with $p < 0.05$ is suggestive of treatment effect heterogeneity.

Hypothesis generating analysis:

The achieved level of ketone in blood immediately prior to exercise is hypothesized to relate to each of the primary outcomes. This hypothesis will be explored graphically and using linear regression models with stratification by treatment sequence.

Power Calculations for Primary Endpoints:

Peak VO_2 : With 18 subjects (9 per treatment sequence), the study has 91% power to detect a mean difference in peak VO_2 (mL/min/kg) between ketone and placebo of 1 mL/min/kg (effect size=0.83), assuming a standard deviation for the difference of 1.2 mL/min/kg.² The power calculation is based on a paired t-test with a two-sided type I error rate of 0.05.

Submaximal Exercise Endurance: Using the effect size noted in a study examining the impact of inorganic nitrate on submaximal exercise endurance in HFpEF,³ a sample size of 18 participants has 88% power to detect an effect size of 0.78, using a paired t-test with a two-sided type I error rate of 0.05, assuming a correlation of 0.8 between measurements on the same individual.

A total of 21 participants were randomized anticipating loss to follow-up of around 3 participants (14%).

References

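### Effect modification by baseline peak VO2 and LVEF is tested only after dichotomising; a continuous term in the same model would be more sensitive to a roughly linear gradient, at no extra parameter

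*SAP*

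**What the plan says.** The base model is in SAP, Primary Analysis: "The primary analysis will regress the difference in outcome for ketone versus placebo on treatment sequence". SAP, Subgroup analyses, extends it: "A term for subgroup will be included in the model described above", with a Wald test of that term and a forest plot.

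Four modifiers are listed. Sex and diabetic status are categorical. Baseline peak VO2 per kg is divided at the sample median ("above versus below median value"). LVEF is divided at a fixed value ("Left ventricular ejection fraction above and below 60" percent), with a literature citation beside it. The SAP does not say which group takes a value exactly at either cut.

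On status, the SAP states: "Subgroup analyses are considered exploratory and thus no formal corrections for multiple comparisons will be used". It then counts eight tests (four modifiers by two primary outcomes), expects 0.4 of them below 0.05 by chance, and reads more than one as suggestive of heterogeneity.

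Neither document plans to analyse peak VO2 or LVEF as a continuous modifier, or discusses doing so. The SAP does plan linear regression on one continuous predictor, the blood ketone level reached before exercise (Hypothesis generating analysis), but that answers a different question.

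**The concern.** Splitting a measured variable treats everyone on one side of the cut as alike, and treats two patients just either side of it as different. If benefit rises or falls steadily with fitness or LVEF, the two-group term captures only part of that gradient. The paired-difference model accepts the measured value with the same single parameter, so the split does not save a degree of freedom.

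What is at stake is sensitivity. Two modifiers by two outcomes means that four of the eight p-values in the heterogeneity rule come from the split form. In an exploratory analysis of about 18 pairs, the main risk is missing a real gradient. In addition, the peak VO2 cut is set by whoever was enrolled, so that subgroup contrast does not carry over directly to another cohort. This last point does not apply to LVEF, whose cut is fixed.

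**Working it through.** **1. Inputs.** From SAP, Power Calculations: 18 pairs (9 per sequence), two-sided alpha 0.05, SD of the within-patient peak VO2 difference 1.2 mL/min/kg, target mean difference 1 mL/min/kg, 21 randomised. From the protocol inclusion criteria: LVEF of at least 50%. The documents do not give the distribution of either modifier, or the size or shape of any modification. These are assumed below and varied.

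**2. The plan's own figures.** Noncentral-t power of a paired t-test with n = 18 (17 df) is 91.3% at effect size 0.83 (stated: 91%) and 87.6% at 0.78 (stated: 88%). Expected chance findings are 8 × 0.05 = 0.4, as stated. 18/(1 − 0.14) gives 21. All reproduce. The documents give no power figure for the subgroup tests.

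**3. Information kept by a split.** For a linear effect this is the squared correlation between the modifier and its two-group indicator.
- Normal modifier, proportion p above the cut: φ(z_p)²/[p(1 − p)]. At the median, 0.3989²/0.25 = 0.637 = 2/π. 18 × 0.637 = 11.5 pairs.
- Uniform modifier on 0 to 1 at the median: covariance 1/8, variances 1/12 and 1/4, so (1/64)/(1/48) = 0.75. 18 × 0.75 = 13.5 pairs.
- LVEF cut at 60%, assuming normal shapes truncated to 50–80%:

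| Share above 60% | Information lost |
|---|---|
| 41% | 33% |
| 51–56% | 35% |
| 64% | 39% |
| 69% | 41% |
| 80% | 51% |

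**4. Power with 18 pairs.** Simulated model: paired difference on sequence plus modifier, t-test with 15 df, normal modifier, linear effect. The correlation is between modifier and paired difference. Repeat runs agree to about one percentage point.

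| Correlation | Continuous | Median split |
|---|---|---|
| 0 (type I error) | 5% | 5% |
| 0.2 | 12% | 10% |
| 0.3 | 22% | 15% |
| 0.5 | 57% | 36% |
| 0.6 | 77% | 52% |
| 0.7 | 92% | 70% |

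For a uniform modifier the gap is narrower: 57% vs 42% at 0.5 and 79% vs 60% at 0.6.

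**5. What these correlations mean.** The slope per SD of the modifier is correlation × 1.2. The difference in benefit between patients at −1 and +1 SD is twice that:
- 0.3: 2 × 0.36 = 0.72 mL/min/kg
- 0.5: 2 × 0.60 = 1.20 mL/min/kg
- 0.6: 2 × 0.72 = 1.44 mL/min/kg

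The last two exceed the 1 mL/min/kg main effect that the trial is sized for. For the split itself, 9 vs 9 with SD 1.2 gives a standard error of 1.2 × √(1/9 + 1/9) = 0.566. With 15 df, 80% power needs a subgroup difference of about 1.7 mL/min/kg.

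**6. If the effect is a step.** With a true step exactly at the cut and correlation 0.6, power is 55% for the continuous term and 82% for the split.

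**The case against.** The strongest reply has four parts.

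- **Shape.** The advantage of the continuous term rests on a roughly straight-line gradient, and the documents do not say which shape holds. Step 6 shows that a step at the cut reverses the ranking. With 18 points, one patient with an extreme value can also drive a slope. This stands. Against it, the SAP gives no reason to expect a step. The peak VO2 cut is simply the sample median, and the LVEF cut carries a citation without an argument for a threshold.
- **Size.** The large gains occur only for strong modification, which no part of the documents supports. At a correlation of 0.3 both tests are weak. This stands: the change does not make the test dependable.
- **Stakes.** The analyses are labelled exploratory, the rule says only suggestive, and type I error is about 5% either way. This stands and limits the importance. It does not remove the point, because the SAP still draws a reading from these p-values.
- **Display.** A p-value from a continuous term may disagree with the split contrast shown in the forest plot. This stands and calls for a label.

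A reader might also infer that about a third of the information is lost for both modifiers. The documents do not support that. The 36% figure is for a normal modifier cut at its median. For LVEF the cut is fixed and the distribution unknown.

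**Conclusion.** The point holds as a low-cost improvement to an exploratory analysis. Under a linear effect and a normal modifier, the median split keeps 64% of the information (75% if uniform). With 18 pairs it lowers power from 57% to 36% at a correlation of 0.5 and from 77% to 52% at 0.6, but only from 22% to 15% at 0.3. For LVEF the loss was 33% to 51% under the shapes tried, all of them assumptions. If more than 18 of the 21 randomised patients complete, the gap remains: with 20 pairs it is 61% vs 40% at 0.5.

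Three stronger inferences are not supported. The continuous term is not better under every shape. The SAP's rule of more than one significant test has not been shown to fail: the figures are per test, only four of its eight tests would change, and power for the rule as a whole was not calculated. Nor do the primary or secondary analyses suffer, since they do not use these terms.

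**What to change.** Amend SAP, Subgroup analyses, before any unblinded analysis:

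- State that the heterogeneity p-values for baseline peak VO2 per kg and LVEF come from the centred continuous value added to the same paired-difference model, and that these are the p-values counted in the heterogeneity rule.
- Keep the median and 60% splits in the forest plot, labelled as descriptive, and say which group takes a value exactly at the cut. That second item is a separate wording gap.
- If a threshold at 60% is believed, give the reason and keep the split as the test for LVEF.

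The cost is a sentence or two. The number of tests, the parameters and the 0.4 expected chance findings are unchanged. The price is an assumed linear trend, sensitivity to a high-leverage patient at this sample size (a plot of the paired difference against the modifier would show it), and a p-value that may not match the displayed contrast. Because the SAP already writes of randomisation and data collection in the past tense, the amendment should record that it was made before unblinding.
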